#### Johns Hopkins Medicine - eForm A

## Clinical utility of handheld hydrogen breathalyzer in identification of non-immune mediated food sensitivities

#### 1. Abstract

Small intestinal bacterial overgrowth (SIBO) is defined as a condition in which an abnormally high amount of coliform bacteria is present in the small bowel and results in premature anaerobic fermentation of carbohydrates before reaching the colon. Commonly recognized causes include gastric achlorhydria, post-surgical bowel stasis, gastrocolic/coloenteric fistulas, and motility disorders leading to bowel stasis. The current "gold standard" for the diagnosis of SIBO, is a breath test that measures the concentration of hydrogen in response to lactulose, a carbohydrate that is only metabolized by bacteria. However, its accuracy is only about 50% and therefore it is not a very useful test, leading most physicians to treat these patients empirically based on clinical suspicion alone. The purpose of this study is to evaluate the clinical utility of a portable medical device called AIRE, an over-the-counter, commercially available handheld breath analyzer that measures exhaled hydrogen content.

**2. Objectives** (include all primary and secondary objectives)

#### **Primary objective:**

To examine the correlation between the results of the AIRE hydrogen and methane breathalyzer and the lactulose hydrogen breath test (LHBT) when performed together in patients clinically suspected to have SIBO.

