#### Secondary objectives:

- 1. To examine the correlation between postprandial exhaled hydrogen and methane (H2) content as measured over a 1-week period by AIRE on the patient's usual diet at home and the results of the standardized LHBT performed in the clinic
- 2. To examine the correlation between AIRE results and gastrointestinal symptoms suggestive of SIBO
- 3. To examine the response of hydrogen and methane breath concentrations using AIRE to antibiotic treatment (in patients undergoing antibiotic treatment).
- 4. To assess the reproducibility of the AIRE results over several weeks in patients not undergoing antibiotic treatment.
- 3. Background (briefly describe pre-clinical and clinical data, current experience with procedures, drug or device, and any other relevant information to justify the research) Small intestinal bacterial overgrowth (SIBO) is defined as a condition in which an abnormally high amount of coliform bacteria is present in the small bowel and results in premature anaerobic fermentation of carbohydrates before reaching the colon. Commonly recognized causes include gastric achlorhydria (ie due to longstanding PPI use), post-surgical bowel stasis, and gastrointestinal motility disorders leading to bowel stasis. Although SIBO is commonly suspected, a major limitation in the field is the lack of a highly accurate test for SIBO. The current gold standard relies on the demonstration of an early rise in breath hydrogen concentration in response to an orally ingested carbohydrate (commonly, lactulose) but its accuracy is about 50%. This may be because it is a one-time snapshot with an artificial substrate. Further, it has to be performed in a clinic, takes up to 5 hours and is relatively expensive. The purpose of this study is to evaluate the clinical utility of a portable medical device called AIRE, which is a validated and commercially available handheld breathalyzer that measures hydrogen and methane content in the breath and connects via Bluetooth to an associated smartphone application to provide immediate results and

Principal Investigator: [name]

Application Number: IRB00204104

visual feedback after use. H2 concentrations determined by the AIRE device showed significant correlation with those measured by LHBT. The AIRE device therefore provides an alternative way to measure exhaled H2 and methane that have the potential for addressing many of the limitations of the standard breath test.

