Healthy volunteers will be asked the Gastrointestinal Symptom Rating Scale (GSRS). This instrument address 15 items combined into five symptom clusters: Reflux, Abdominal pain, Indigestion, Diarrhea and Constipation. The reliability and validity of the GSRS are well-documented, and norm values for a general population are available. The original questionnaire is an interview-based rating scale but has been modified to become a self-administered questionnaire. Takes approximately 3-5 minutes Recall period is past week. Each item is rated on a 7-point Likert scale.

Following a week of AIRE measurement, participants will then undergo the physician-ordered and clinically indicated LHBT done on the clinically scheduled day and time. They will use the AIRE device one time immediately before the LHBT begins and throughout the lactulose breath test as well, at the same intervals as the lactulose breath test (breathe into AIRE device immediately after breathing into the standard lactulose breath test tube).

Subjects will be notified of the breath test result and whether or not they will receive antibiotics. This will be the only result for disclosure to the participant. Decisions regarding treatment will be based on clinical judgment and standard of care, after taking into consideration the patient's history and test results. This decision will be made by the care provider (MD or mid-level) and will be discussed with the patient by a member of the study team.

A Lactulose challenge using the AIRE device will be repeated after 5 - 7 days of the initial LHBT if this reports negative findings for SIBO. We are testing the hypothesis that repeating the test will increase the probability of a positive response.

If subjects receive antibiotic treatment, they will be asked to use the AIRE device three days before they begin taking antibiotics, during treatment, and for four weeks after treatment ends.

One month later (if no antibiotics were prescribed) participants will repeat the 1-week use of AIRE device described above. Therefore, all participants will complete this second week of AIRE use regardless whether or not they received antibiotics. A second round of antibiotics will be prescribed if the patient does not response to the initial treatment based on the attending physician decision.

Once the second week of AIRE use is completed, participants will return the AIRE machine. Data from the app is automatically downloaded from the app to the Food Marble server.

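### Correlation is the only method named for the same-session AIRE versus LHBT readings, and it cannot show whether the two tests agree

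*Combined protocol and SAP*

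**What the plan says.** Under 2. Objectives, the primary objective is "To examine the correlation between the results of the AIRE hydrogen and methane breathalyzer and the lactulose hydrogen breath test (LHBT", for tests performed together in patients with suspected SIBO. The type of coefficient is not stated.

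Study Procedures makes this a paired design. AIRE is used at every LHBT sampling time, and patients "breathe into AIRE device immediately after breathing into the standard lactulose breath test tube". The same section treats the result as positive or negative. The lactulose test "using the AIRE device will be repeated after 5 - 7 days of the initial LHBT if this reports negative findings for SIBO", and the stated reason is: "We are testing the hypothesis that repeating the test will increase the probability of a positive response". No positivity rule is given for either test.

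Section 6, Study Statistics, again names correlation. Its other references to comparing AIRE with the clinic test name no method. The same section says that the comparison with the commercial test is nearly complete and that the data have had an initial look.

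3. Background reports that hydrogen "concentrations determined by the AIRE device showed significant correlation with those measured by LHBT", and then draws an inference from this: "The AIRE device therefore provides an alternative way to measure exhaled H2 and methane that have the potential for addressing many of the limitations".

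Nowhere do the documents name a mean difference, limits of agreement, a concordance coefficient, percent agreement or kappa.

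**The concern.** Two instruments sampling nearly the same breath at the same moments form a method-comparison study. The natural questions are whether they read the same level and whether they classify the same patients as positive. Correlation answers neither. It shows only whether patients who are high on one test tend to be high on the other.

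This matters inside the trial. In the repeat challenge the qualifying negative result comes from LHBT and the second result from AIRE. A switch from negative to positive therefore mixes the effect of repeating with any difference between devices. The AIRE readings from the first session would help to separate these, but the plan does not say that they will be used.

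The objectives on symptoms, antibiotic response and reproducibility of AIRE are not affected. The documents also differ on which AIRE–LHBT comparison is primary. That is a separate matter, and this point concerns the same-session readings whichever is primary.

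**Working it through.** **1. The plan's own figure.** Study Statistics gives 100 patients for r = 0.5, alpha 0.05, beta 0.20. By Fisher's z, two-sided, n = ((1.960 + 0.842)/atanh(0.5))² + 3 = (2.802/0.549)² + 3 ≈ 29. The stated inputs do not reproduce 100, although 100 is more than enough. The sentence is written for the home-week readings, and nothing below depends on it.

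**2. Invariance (no assumptions about the data).** For k > 0, corr(X, kY) = k·cov(X, Y)/(SD_X · k·SD_Y) = corr(X, Y). Ranks are also unchanged, so Spearman's coefficient is too. A concordance or intraclass coefficient would respond to k, but none is named.

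**3. What a scale error could do (illustration).** The documents supply none of these inputs, so all are assumed:
- a rise-from-baseline cut-off of 1, the same for both devices;
- lognormal rise with log-SD 0.5, 0.8 or 1.2, centred so that 20%, 30% or 50% are LHBT-positive;
- lognormal baseline with median 0.3 and log-SD 0.6, and peak = baseline + rise;
- AIRE baseline and peak = k × value × exp(noise), with independent noise SD 0.1 or 0.2, and LHBT taken as noise-free.

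Ranges are over log-SD and noise, with 1,000,000 simulated patients per setting.

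| Share reading positive on AIRE | 20% LHBT+ | 30% LHBT+ | 50% LHBT+ |
|---|---|---|---|
| LHBT positives, k = 0.5 | 8–41% | 11–47% | 18–57% |
| LHBT positives, k = 0.7 | 33–65% | 39–69% | 49–77% |
| LHBT positives, k = 1 | 78–94% | 80–95% | 84–96% |
| LHBT negatives, k = 1 | 2–10% | 2–13% | 4–17% |
| LHBT negatives, k = 1.3 | 9–27% | 12–32% | 18–40% |

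Pearson r of the rises is 0.84–0.99 and Spearman 0.81–0.99 over all settings, and neither changes with k. Overall agreement moves less than detection: at 30% LHBT-positive it is 82–91% with k = 0.7 and 85–97% with k = 1.

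**4. When the effect vanishes.** If AIRE has its own cut-off, rescaled by the same k, then k·rise ≥ k·c is the same event as rise ≥ c, and the results return to the k = 1 rows. A constant offset cancels in a rise from baseline.

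**5. The repeat challenge.** Only LHBT-negative patients repeat. First-session AIRE is correlated with that LHBT, so these patients are selected on a low day. With no true change, an illustration takes AIRE positivity from about 4% in the first session to about 8–22% at the repeat, depending on the day-to-day variation assumed.

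**6. Precision available (n = 100, one pair per patient).** Each limit of agreement has a 95% half-width of 1.96·√(3/100) = 0.34 SD of the differences. Wilson 95% intervals for an observed 90% agreement:
- 18/20: 70–97%
- 27/30: 74–97%
- 45/50: 79–96%
- 63/70: 81–95%
- 72/80: 81–95%
- 90/100: 83–95%

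**The case against.** The study is described as a pilot, its stated aim is to examine a correlation, and no objective claims interchangeability or diagnostic accuracy. The protocol puts LHBT accuracy at about 50%, so agreement with LHBT says little about true SIBO, and it calls AIRE validated. The scale errors in the illustration are invented, and the detection figures depend on forcing one cut-off on both devices. Detection among positives is also the measure most sensitive to under-reading. The model uses one baseline and one peak, whereas the clinic test "relies on the demonstration of an early rise in breath hydrogen concentration in response to an orally ingested carbohydrate" and is read serially.

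Much of this stands. The percentages are not forecasts, scale error alone could be corrected by calibration, and overall agreement should be shown beside detection. What does not fall is the invariance in step 2, which needs none of these assumptions. Whether two devices sampled together agree is also a fair question however accurate LHBT is for SIBO, and the only evidence for AIRE that the Background describes is itself a correlation.

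A reader might go further and infer that AIRE under-reads, or that the trial plans to declare AIRE interchangeable with LHBT. The documents support neither. They report no readings, and the Background sentence on an alternative way to measure concerns existing data and is hedged.

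**Conclusion.** The point holds as a gap in the analysis that is cheap to close. As written, the plan cannot show a proportional bias between AIRE and LHBT or how often the two give the same result, although the paired readings are taken and the repeat challenge needs a positive/negative reading on AIRE.

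The size is unknown. The central illustration is 39–69% against 80–95% of LHBT positives detected, and 82–91% against 85–97% overall agreement, for AIRE reading 30% low with 30% LHBT-positive. It rests on an assumed scale error, assumed distributions and a common cut-off, and it disappears if the AIRE cut-off is rescaled to match.

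A reader might also infer that setting the first-session AIRE result beside the repeat AIRE result would isolate the effect of repeating. It would not. It removes the change of device but leaves regression to the mean from selecting LHBT-negative patients, so a rise in positivity is not by itself evidence that repeating helps.

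**What to change.** Keep correlation as a descriptive result and name the coefficient. For the same-session readings, add:

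(a) Bias and 95% limits of agreement with 95% CIs, from paired differences with a patient random effect, on the log/ratio scale if differences grow with level. Do this for hydrogen, and for methane only if the clinic test reports it; the Abstract describes LHBT as "a breath test that measures the concentration of hydrogen in response to lactulose". This needs numeric LHBT values in units matching AIRE, which the documents do not confirm are available.

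(b) One result per patient: positive, negative and overall percent agreement and kappa, with 95% CIs. The main analysis applies the clinic's own LHBT positivity definition to both devices. A sensitivity analysis uses any AIRE-specific rule fixed in advance, or a cut-off rescaled by the estimated bias and labelled as data-derived.

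(c) For the repeat challenge, compare the AIRE repeat with the first-session AIRE result in the same patients, and state the regression-to-the-mean limitation alongside the result.

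Report all of this as estimation of agreement with LHBT, not with true SIBO. Date the change and label it as specified after the initial look at the data described in Study Statistics.

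Cost: no new patients, visits or devices. If numeric LHBT values cannot be had, (a) and the bias-rescaled cut-off drop out. The rest of (b), and (c), can still use the clinic's positive/negative report, provided AIRE reports in the units of the clinic's rule. The downsides are some extra analysis, a possibly less favourable headline, and late specification.

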#### Secondary objectives:

- 1. To examine the correlation between postprandial exhaled hydrogen and methane (H2) content as measured over a 1-week period by AIRE on the patient's usual diet at home and the results of the standardized LHBT performed in the clinic
- 2. To examine the correlation between AIRE results and gastrointestinal symptoms suggestive of SIBO
- 3. To examine the response of hydrogen and methane breath concentrations using AIRE to antibiotic treatment (in patients undergoing antibiotic treatment).
- 4. To assess the reproducibility of the AIRE results over several weeks in patients not undergoing antibiotic treatment.
- 3. Background (briefly describe pre-clinical and clinical data, current experience with procedures, drug or device, and any other relevant information to justify the research) Small intestinal bacterial overgrowth (SIBO) is defined as a condition in which an abnormally high amount of coliform bacteria is present in the small bowel and results in premature anaerobic fermentation of carbohydrates before reaching the colon. Commonly recognized causes include gastric achlorhydria (ie due to longstanding PPI use), post-surgical bowel stasis, and gastrointestinal motility disorders leading to bowel stasis. Although SIBO is commonly suspected, a major limitation in the field is the lack of a highly accurate test for SIBO. The current gold standard relies on the demonstration of an early rise in breath hydrogen concentration in response to an orally ingested carbohydrate (commonly, lactulose) but its accuracy is about 50%. This may be because it is a one-time snapshot with an artificial substrate. Further, it has to be performed in a clinic, takes up to 5 hours and is relatively expensive. The purpose of this study is to evaluate the clinical utility of a portable medical device called AIRE, which is a validated and commercially available handheld breathalyzer that measures hydrogen and methane content in the breath and connects via Bluetooth to an associated smartphone application to provide immediate results and

Principal Investigator: [name]

Application Number: IRB00204104

visual feedback after use. H2 concentrations determined by the AIRE device showed significant correlation with those measured by LHBT. The AIRE device therefore provides an alternative way to measure exhaled H2 and methane that have the potential for addressing many of the limitations of the standard breath test.

#### **Study Procedures**

This pilot study will be an open-label trial in patients suspected to have SIBO (abdominal bloating, distention, discomfort, change in bowel movements) and who are being considered for diagnostic testing using the lactulose-hydrogen breath test (LHBT). 150 patients will be accrued from the gastroenterology motility clinic or the scleroderma clinic, in addition, 20 healthy volunteers will be accrued making a grand total of 120 participants. Healthy volunteers will be recruited initially at the Ross Research Building. Other alternatives provided by The Recruitment Innovation Unit (RIU) from the Institute for Clinical & Translational Research (ICTR) Johns Hopkins Medicine may be considered to make our study more visible within Hopkins community. If the subject meets eligibility criteria, and the LHBT has been scheduled, a co-investigator will contact the patient to schedule a study visit with a research coordinator and obtain a written consent. Potential subjects will be provided with a copy of the Informed Consent form prior to the remote consent meeting either via email, fax, mail or previously provided during an in person visit. Potential subjects will then be contacted by phone by a study team member who is a consent designee to review the consent form in detail. Potential subjects will be given adequate time to consider the research study and ask questions prior to signing the consent form. The potential subject will then sign and date/time the informed consent document and it will be mailed, emailed or faxed to the consent designee, who will also sign/date/time. A copy of the fully signed consent form will be returned to the volunteer. The contact and screening information of patients that are successfully recruited will be documented, placed in the participant's study folder and stored in a locked cabinet in the motility clinic at Bayview. Any information documented during the screening process for patients who do not meet basic eligibility criteria or do not wish to participate will be immediately destroyed.

The study coordinator will maintain a list of all participants, each having a unique participant code, e.g. JH-SIBO1-001, along with various personally identifiable information, e.g. email, name etc. The coordinator will instruct the participant to use the participant code to sign up for the app from FoodMarble. FoodMarble however, we would never receive participant's email address or any information (the participant code is all they would have on their servers to identify the participant).

Enrolled patients will be provided the AIRE device and will be instructed on how to use the device as well as the accompanying phone application. Participants will eat their normal, typical diets during the first week of the study. They will use the AIRE machine to measure exhaled H2 and Methane content before and after two meals each day – the first meal of the day and the last meal of the day. They will breathe into the AIRE machine before eating to obtain a baseline value. Once they have finished eating, they will breathe into the AIRE machine 30 minutes, 60 minutes, and 90 minutes postprandially. The exhaled H2 and Methane results will be automatically recorded in the phone application, which is connected to the AIRE machine via Bluetooth. The participants will record their food intake and symptoms directly into their smartphone via an app that comes with the AIRE device. Symptom scores will be recorded at the same time they use the AIRE machine (30 minutes, 60 minutes, and 90 minutes postprandially). Note participants will be asked to not use the AIRE device after a meal including alcohol as this will skew the device results, however patients will be asked to record all meal content (including meals with alcohol) in their food log throughout the duration of the study.

Symptomatic participants will be asked to complete the Gastrointestinal Symptom Rating Scale for Irritable Bowel Syndrome (GSRS-IBS). The GSRS IBS is a 13-item reliable, valid and user-friendly instrument with excellent psychometric properties measuring. Depicting problems with satiety, abdominal pain, diarrhea,

Principal Investigator: [name]

Application Number: IRB00204104

constipation and bloating. The internal consistency reliability was high, ranging from 0.74 (pain) to 0.85 (satiety). Takes approximately 3-5 minutes. Recall period is past week Each item is rated on a 7-point Likert scale.

Healthy volunteers will be asked the Gastrointestinal Symptom Rating Scale (GSRS). This instrument address 15 items combined into five symptom clusters: Reflux, Abdominal pain, Indigestion, Diarrhea and Constipation. The reliability and validity of the GSRS are well-documented, and norm values for a general population are available. The original questionnaire is an interview-based rating scale but has been modified to become a self-administered questionnaire. Takes approximately 3-5 minutes Recall period is past week. Each item is rated on a 7-point Likert scale.

Following a week of AIRE measurement, participants will then undergo the physician-ordered and clinically indicated LHBT done on the clinically scheduled day and time. They will use the AIRE device one time immediately before the LHBT begins and throughout the lactulose breath test as well, at the same intervals as the lactulose breath test (breathe into AIRE device immediately after breathing into the standard lactulose breath test tube).

Subjects will be notified of the breath test result and whether or not they will receive antibiotics. This will be the only result for disclosure to the participant. Decisions regarding treatment will be based on clinical judgment and standard of care, after taking into consideration the patient's history and test results. This decision will be made by the care provider (MD or mid-level) and will be discussed with the patient by a member of the study team.

A Lactulose challenge using the AIRE device will be repeated after 5 - 7 days of the initial LHBT if this reports negative findings for SIBO. We are testing the hypothesis that repeating the test will increase the probability of a positive response.

If subjects receive antibiotic treatment, they will be asked to use the AIRE device three days before they begin taking antibiotics, during treatment, and for four weeks after treatment ends.

One month later (if no antibiotics were prescribed) participants will repeat the 1-week use of AIRE device described above. Therefore, all participants will complete this second week of AIRE use regardless whether or not they received antibiotics. A second round of antibiotics will be prescribed if the patient does not response to the initial treatment based on the attending physician decision.

Once the second week of AIRE use is completed, participants will return the AIRE machine. Data from the app is automatically downloaded from the app to the Food Marble server.

Data analysis will be performed at Mayo Clinic Scottsdale, Arizona by [name], ([contact]). This site will no recruit participants.

Johns Hopkins will serve as coordinating center under supervision of [name], responsible for overall data management, monitoring and communication, and general oversight of the conduct of this protocol.

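### No order is set between the in-app symptom score and the AIRE breath, so if readings are seen and these scores serve secondary objective 2, part of the AIRE-symptom correlation could come from seeing the reading

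*Combined protocol and SAP*

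**What the plan says.** Study Procedures schedules four breaths around each measured meal. The first is before the meal: "They will breathe into the AIRE machine before eating to obtain a baseline value". The others follow at 30, 60 and 90 minutes. Symptoms go into the device's own app: "The participants will record their food intake and symptoms directly into their smartphone via an app that comes with the AIRE device". On timing, the text says "Symptom scores will be recorded at the same time they use the AIRE machine" and lists only the three post-meal points. No order is given, and no pre-meal symptom score is listed.

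Section 3 (Background) says that the device "connects via Bluetooth to an associated smartphone application to provide immediate results" and gives "visual feedback after use". The blinding item says that none is indicated. Section 8 (Benefits) expects participants to learn about their food tolerances by using the device. One sentence in Study Procedures, after the LHBT paragraph, limits disclosure to a single result. It does not say whether the limit covers AIRE readings shown in the app.

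Secondary objective 2 is "To examine the correlation between AIRE results and gastrointestinal symptoms suggestive of SIBO". It names neither the AIRE measure nor the symptom measure. Patients also complete the GSRS-IBS, which has past-week recall and no stated completion day. Section 6 (Study Statistics) gives no analysis for objective 2.

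**The concern.** A symptom score is a subjective rating. If a participant first sees a gas reading and then rates bloating or pain on the same phone, the reading can shape the rating. A high value may prompt a higher score, or a participant may react against it, so the direction is not known. Objective 2 would then correlate a reading with a score that the reading had helped to produce. Nothing in the planned analysis could separate this from a true link between gas and symptoms. Order cannot be imposed after the data are collected, and the documents do not say whether the app stores the order of entry.

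**Working it through.** **Passages side by side.** Three conditions must all hold for the bias to arise.

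1. Objective 2 uses the in-app scores. This is open, because the GSRS-IBS is the other candidate.
2. It uses the home readings. This is also open, because AIRE is used during the LHBT as well, and no in-app symptom score is described there.
3. Participants see a reading before they score. The Background and Benefits text make sight of readings likely. The disclosure sentence could point the other way.

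**What is outside the concern.** Section 2 states the primary objective as AIRE against LHBT performed together. Section 6 states it as home AIRE readings against LHBT. Both compare gas with gas and use no symptom score.

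**Counts from the schedule, one home week.**
- Breaths: 7 days x 2 meals x 4 = 56 at most (fewer if meals include alcohol).
- Breaths with a score at the same time point: 7 x 2 x 3 = 42.
- Pre-meal breaths with no score: 7 x 2 = 14.

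**Size.** The plan has no figure for objective 2 to reproduce; its only power statement concerns AIRE against LHBT. What follows is an illustration, and every input is an assumption. There is no true link. The score moves s SD per 1 SD of the reading last seen, plus unit independent noise. Successive readings within a meal follow an AR(1) pattern with correlation ρ. A share c of the influence persists to the next time point.

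*Single pairs, breath first:* r = s/√(1+s²).
- s = 0.1: 0.1/√1.01 = 0.0995
- s = 0.2: 0.2/√1.04 = 0.196

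Negative s gives the same sizes with a minus sign.

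*Single pairs, score first:* r = scρ/√(1+(sc)²), for ρ = 0.3 / 0.5 / 0.8.
- c = 0: zero
- c = 0.5: 0.015 / 0.025 / 0.040 (s = 0.1); 0.030 / 0.050 / 0.080 (s = 0.2)
- c = 1: 0.030 / 0.050 / 0.080 (s = 0.1); 0.059 / 0.098 / 0.157 (s = 0.2)

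*Per-patient averages.* Let readings also differ stably between patients, with share B of their variance, over 14 meals with 3 scored points each. Then:
- V = B + (1−B)(3+4ρ+2ρ²)/126 is the variance of the mean post-meal reading.
- K = B + (1−B)(2+4ρ+2ρ²+ρ³)/126 is its covariance with the mean of the readings one time point earlier.
- Noise in the mean score has variance 1/42.
- Breath first: r = s√V/√(s²V+1/42).
- Score first: r = scK/√(V(s²c²V+1/42)).

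Take s = 0.1, B = 0.2, ρ = 0.5. V = 0.2 + 0.8 x 5.5/126 = 0.2349, and K = 0.2 + 0.8 x 4.625/126 = 0.2294. Breath first gives r = 0.300. Score first gives 0.293 at c = 1 (2.4% lower) and 0.151 at c = 0.5 (about 50% lower).

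Over s = 0.1 or 0.2, B = 0.2 or 0.5 and ρ = 0.3, 0.5 or 0.8, breath-first r runs from 0.30 to 0.69. The order rule removes under 3% of it at c = 1 and 38% to 50% at c = 0.5. The averaged r is larger than the single-pair r because averaging shrinks the assumed independent noise. Stable differences between patients in symptom level would make it smaller.

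*Consequence for a test.* Suppose objective 2 used one value per patient and the spurious r were 0.0995 or 0.196 with 100 patients. Then atanh(r) x √97 = 0.98 or 1.96, and the chance of two-sided p < 0.05 is about 17% or 50%.

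**The case against.** The strongest case against is that the harm is conditional throughout. Objective 2 may relate LHBT-day AIRE results to the GSRS-IBS, in which case the order of home entries hardly matters. The disclosure sentence may mean that AIRE readings are not shown. The order may also be set in training: patients are to be instructed on the device and app, and those instructions are not in the documents. Section 6 says the original aim is almost completed. Study Procedures gives 150 patients plus 20 volunteers but a total of 120, and Section 6 speaks of 70 further patients in one place and 50 in another. The number still to be enrolled is therefore unclear.

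All of this stands as a limit on strength. It does not remove the point, because the plan neither sets the order nor clearly hides the readings.

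Two further objections stand in full. Scoring first leaves the influence of readings already seen, so a reader should not infer from the single-pair figures that the order rule removes a predictable share of the bias; the averaged case shows that it may remove almost none. Nor should a reader infer that the missing pre-meal score causes this bias. It only leaves symptoms without a baseline, and a pre-meal score would still follow readings from earlier meals.

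**Conclusion.** The point holds as a conditional weakness in secondary objective 2 that is cheap to reduce. If the in-app scores and home readings serve that objective, and participants see the readings, part of the correlation could come from seeing them. Size and direction are unknown; the figures above rest on assumed s, c, ρ and B that no document gives.

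A reader might infer that the AIRE-symptom correlation will be spurious, or that the AIRE-LHBT comparison is compromised. The documents support neither. They do not establish that readings are seen before scoring or that these scores are the measure for objective 2, and the primary comparison uses no symptom scores.

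**What to change.** 1. First reconcile the disclosure sentence in Study Procedures with the Background and Benefits sections, so that the plan says whether participants see AIRE readings.
2. Unless readings are hidden, change Study Procedures for participants still to be enrolled so that the symptom score is saved before the breath at each time point.
3. Name the AIRE measure and the symptom measure for objective 2.
4. Flag participants who used the present procedure, and run a sensitivity analysis on that flag.
5. State as a limitation that readings already seen can still influence scores. The order rule is therefore a partial remedy and may do little for per-patient averages if that influence persists.

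A pre-meal symptom score for patients is a separate, optional addition. It gives symptoms a baseline at a cost of at most 7 x 2 = 14 short entries per home week.

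The required changes cost one instruction, one clarified sentence, two named measures and a flag, with no new visits. The downsides are two entry procedures in the data and residual carry-over from earlier readings.
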